8.1.2.2 Procedures for Recording Adverse Events

HCPs should use correct medical terminology/concepts and MedDRA coding when recording AEs in the AE section of the CRF. Colloquialisms and abbreviations should be avoided.

Only one AE term should be recorded in the event field of the CRF.

See Appendix 3 for further specific instruction regarding:

- Infusion-Related Reactions
- Diagnosis versus signs and symptoms

- Adverse Events occurring secondary to other Adverse Events
- Persistent or recurrent Adverse Events
- Abnormal Laboratory Values
- Abnormal Vital Sign Values
- Abnormal Liver Function Tests
- Deaths
 - All events with an outcome or consequence of death should be classified as serious adverse events (SAEs) and reported to the marketing authorization holder immediately. In certain circumstances, however, suspected adverse reactions with fatal outcome may not be subject to expedited reporting. (~~see Section 8.3~~). All deaths that occur during the protocol-specified AE reporting period, regardless of relationship to study medicine, must be recorded in the AE section of the CRF and immediately reported to the marketing authorization holder. *Deaths that are clearly attributable to disease progression must not be reported as an AE*
- Pre-existing Medical Conditions
- Lack of Therapeutic Efficacy
- Hospitalization or Prolonged Hospitalization
- Overdoses, Misuses, Abuses, Off-Label Use, Occupational Exposure, or Medication Error (SS: *Special Situation*)
- Quality Defects, Falsified Medicinal Products and *Product Complaints*
- Drug Interactions

8.1.3 Reporting Requirements from Healthcare Professional to Marketing Authorization Holder

8.1.3.1 Immediate Reporting Requirements from Healthcare Professional to Marketing Authorization Holder

Certain events require immediate reporting to allow the Marketing Authorization Holder and the regulatory authorities to take appropriate measures to address potential new risks associated with the use of the medicine. The HCP must report such events to the marketing authorization holder immediately; under no circumstances should reporting take place more than 24 hours after the HCP learns of the event. The following is a list of events that the HCP must report to the marketing authorization holder within 24 hours after learning of the event, regardless of relationship to study medicine:

- SAEs
- Non-serious AESI
- Pregnancies

The HCP must report new significant follow-up information for these events to the marketing authorization holder immediately (i.e., no more than 24 hours after becoming aware of the information). New significant information includes the following:

- New signs or symptoms or a change in the diagnosis
- Significant new diagnostic test results
- Change in causality based on new information
- Change in the event's outcome, including recovery
- Additional narrative information on the clinical course of the event

For reports of SAEs and non-serious AESI, including follow-up, HCPs should record all case details that can be gathered immediately (i.e., within 24 hours) in the AE page of the CRF and submit the report via the EDC system. A report will be generated and sent to Roche Drug Safety by the EDC system.

In the event that the EDC system is temporarily unavailable, please refer to Section 8.1.3.3.

HCPs must also comply with local requirements for reporting SAEs to the local health authority and IRB/EC.

8.1.3.2 Reporting Requirements for Non-Serious Adverse Events

For all non-serious AEs, including follow-up reports, HCPs must record all case details that can be gathered within 30 calendar days of learning of the event on the AE section of the CRF and submit the report via the EDC system. A report will be generated and sent to Roche Drug Safety to allow appropriate reporting to relevant competent authorities.

In the event that the EDC system is temporarily unavailable, please refer to Section 8.1.3.3.

8.1.3.3 If EDC System is Temporarily Unavailable

In the event that the EDC system is temporarily unavailable, a completed paper reporting form and fax coversheet should be faxed/scanned to Roche Drug Safety or its designee immediately (i.e., no more than 24 hours after learning of the event) or within 30 calendar days for non-serious AEs if not AESI, using the fax number or email address provided to physicians.

Once the system is available again, all information should additionally be entered and submitted via the EDC system.

8.1.3.4 Reporting Requirements for Pregnancies/Breastfeeding

Pregnancies/Breastfeeding in Female Patients

Female patients of childbearing potential will be instructed to immediately inform the physician if they become pregnant during the study or within 5 months after the last dose of medicine. A Pregnancy Report should be completed by the physician immediately (i.e., no more than 24 hours after learning of the pregnancy) and sent to Roche Drug Safety. Pregnancy should not be recorded on the AE eCRF. The physician should discontinue Obinutuzumab and counsel the patient, discussing the risks of the pregnancy and the possible effects on the fetus. Monitoring of the patient should continue until conclusion of the pregnancy. Any SAEs associated with the pregnancy (e.g., an event in the foetus, an event in the mother during or after the pregnancy, or a congenital anomaly/birth defect in the child) should be reported on the AE section of the eCRF.

Suspected adverse reactions that occur in infants following exposure to a medicinal product from breast milk should be reported to Roche Drug Safety.

Pregnancies in Female Partners of Male Patients ~~Male patients will be instructed through the Informed Consent Form to immediately inform the physician if their partner becomes pregnant during the study or within 5 months after the last dose of study medicinal product. A Pregnancy Report should be completed by the physician immediately (i.e., no more than 24 hours after learning of the pregnancy) and sent to Roche Drug Safety. Attempts should be made to collect and report details of the course and outcome of any pregnancy in the partner of a male patient exposed to study medicine. The pregnant partner will need to sign an Authorization for Use and Disclosure of Pregnancy Health Information to allow for follow-up on her pregnancy. Once the authorization has been signed, the physician will update the Pregnancy Report with additional information on the course and outcome of the pregnancy. A physician who is contacted by the male patient or his pregnant partner may provide information on the risks of the pregnancy and the possible effects on the fetus, to support an informed decision in cooperation with the treating physician and/or obstetrician.~~

Abortions

Any abortion should be classified as an SAE (as the marketing authorization holder considers abortions to be medically significant), recorded in the AE section of the eCRF, and reported to the marketing authorization holder immediately (i.e., no more than 24 hours after learning of the event; see Section 8.1.3.1).

Congenital Anomalies/Birth Defects

Any congenital anomaly/birth defect in a child born to a female patient exposed to the medicine should be classified as an SAE, recorded in the AE section of the eCRF, and reported to the marketing authorization holder immediately (i.e., no more than 24 hours after learning of the event; see Section 8.1.3.1).

8.1.3.5 Reporting Requirements for Adverse Events originating from Patient Reported Outcomes

Although physicians are not expected to review the PRO data, if HCP/study personnel becomes aware of a potential adverse event during review of the PRO questionnaire data, he/she will determine whether the criteria for an adverse event have been met and, if so, these must be reported using the Adverse Event eCRF.

8.1.4 Follow-Up of Patients after Adverse Events

8.1.4.1 HCP Follow-Up

The HCP should follow each AE until the event has resolved to baseline grade or better, the event is assessed as stable by the HCP, the patient is lost to follow-up, or the patient withdraws consent. Every effort should be made to follow all SAEs considered to be related to studied medicinal product until a final outcome can be reported.

During the study period, resolution of AEs (with dates) should be documented in the AE section of the eCRF and in the patient's medical record to facilitate SDV.

All pregnancies reported during the study should be followed until pregnancy outcome.

8.1.4.2 Marketing Authorization Holder Follow-Up

For all AEs, the MAH or a designee may follow up by telephone, fax, electronic mail, and/or a monitoring visit to obtain additional case details and outcome information (e.g., from hospital discharge summaries, consultant reports, autopsy reports) in order to perform an independent medical assessment of the reported case. AE follow-up should be documented in the AE section of the eCRF.

8.2 SAFETY REPORTING REQUIREMENTS FOR NON-STUDIED PRODUCTS

Although adverse event information is not being actively solicited for non-studied products, the physician/consumers are reminded to report any adverse reactions (for which they suspect a causal role of a product) that come to their attention to the marketing authorization holder of the suspected product, or to the concerned competent authorities via the national spontaneous reporting system.

In addition, the following should also be reported if occurring during exposure to a marketed medicinal product, even in the absence of adverse events:

- Pregnancy
- Breastfeeding
- Abnormal laboratory findings
- Overdose, abuse, misuse, off-label use, medication error or occupational exposure
- Reports of lack of efficacy
- Product quality defects and falsified medicinal products

- Data related to a suspected transmission of an infectious agent via a medicinal product
- Drug interactions (including drug/drug, drug/food, drug/device and drug/alcohol)

When a patient is not exposed to a marketed medicinal product, but the HCP/consumer becomes aware of the potential for a medication error, or an intercepted medication error, this should also be reported.

8.3 *REPORTING OF PRODUCT COMPLAINTS WITHOUT ADVERSE EVENTS*

Report Roche product complaints without Adverse Events, where Product Complaint is any written or oral information received from a complainant that alleges deficiencies related to Identity, Quality, Safety, Strength, Purity, Reliability, Durability, Effectiveness, or Performance of a product after it has been released and distributed to the commercial market, to [contact]. Reports can be done via mail, clearly stating the product, protocol number, description of the complaint. Report non-Roche-product complaints as per local regulation.

9. PUBLICATION OF DATA AND PROTECTION OF TRADE SECRETS

Regardless of the outcome of a study, the sponsor is dedicated to openly providing information on the study to healthcare professionals and to the public, both at scientific congresses and in peer-reviewed journals. The sponsor will comply with all requirements for publication of study results.

The results of this study may be published or presented at scientific meetings. If this is foreseen, the physician must agree to submit all manuscripts or abstracts to the sponsor prior to submission for publication or presentation. This allows the sponsor to protect proprietary information and to provide comments based on information from other studies that may not yet be available to the physician.

In accordance with standard editorial and ethical practice, the sponsor will generally support publication of multicenter studies only in their entirety and not as individual center data. In this case, a coordinating physician will be designated by mutual agreement.

Authorship will be determined by mutual agreement and in line with International Committee of Medical Journal Editors' authorship requirements. Any formal publication of the study in which contribution of sponsor personnel exceeded that of conventional monitoring will be considered as a joint publication by the physician and the appropriate sponsor personnel.

Any inventions and resulting patents, improvements, and/or know-how originating from the use of data from this study will become and remain the exclusive and unburdened property of the sponsor, except where agreed otherwise.

Data Collection (available data will be collected; no additional diagnostic or monitoring procedures will be applied to patients outside of routine clinical practice)	Enrolment visit ^a	Retrospective Data collection	Prospective Data Collected during Treatment Period (Induction and maintenance period)	Follow-up period ^b
Informed consent ^c	x			
Diagnosis confirmation (clinical stage, histology)		x		
Target Population	x	x		
Medical history and demographic data		x		
Concomitant treatments/medications ^d	x	x	x	
Treatment with Obinutuzumab	(x) ^e	(x) ^c	x	
Prophylaxis medication	x	x	x	
Laboratory assessments ^e	x	x	x	
Pregnancy test	x ^f	x ^f	x ^f	
Physical examination and Vital signs	x	x	x	
ECOG	x	x	x	x
B symptoms	x	x	x	x
QoL (Quality of life: EuroQol 5-Dimension Questionnaire, 5-level version (EQ-5D-5L); Functional Assessment of Chronic illness Therapy-Lymphoma (FACT-Lym) ^g	x		x	*
Chemotherapy regimen	x	x	x	
AEs/SAEs/AESI/SSIRR/ADR	x		x	x ^k
Retrospective Safety data collection		x ^h		
Tumor assessments	x	x	x	x
Ann Arbor	x	x		
FLIPI score assessment ⁱ	x	x		
BM evaluation	x	x	x	x
Response rate ^j	x	x	x	x
New anti-cancer therapy and survival status after end of treatment				x

^a Items Concomitant treatments/medications, Treatment with obinutuzumab, Pregnancy test. Physical examination and Vital signs, Prophylaxis medication and Chemotherapy regimen apply only for patients still on treatment at the time of enrollment as part of their standard procedures for treatment. In case of patients

enrolled after treatment completion, these data will be collected as indicated in the Retrospective column and the prospective information will be collected as described in the Follow-up period.

^b Approximately one-year follow-up after last dose of Obinutuzumab administration, as per clinical practice, or for patients that early discontinue the treatment up to 3.5 years after first treatment administration or until withdrawal of consent, study termination by the Sponsor, or death, whichever occurs first, regardless of whether patients start a new anti-cancer therapy. For patients that discontinue treatment before completing induction or maintenance, the follow up parameters can be collected in accordance with current patient's schedule visit and not every 2 months. Follow-up data will include at least tumor assessments, *new anti-lymphoma therapy informations*, and safety data.

^c Patients included should have performed at least 2 cycles of induction treatment with Obinutuzumab and chemotherapy, within 1 year from beginning of treatment

^d Including any medication used by the patient from 7 days prior to starting treatment with obinutuzumab.

^e Laboratory tests will include: haematology (WBCs and differential count [at least neutrophils and monocyte %], RBCs, haemoglobin, haematocrit, platelet count) and blood chemistry (creatinine, beta-2 microglobulin, LDH, AST, ALT).

^f Data collected if performed per clinical practice as clinically indicated.

^g QoL will be completed prospectively period, every 2 cycles in induction treatment phase and every 2 months during maintenance treatment phase. For further instructions over QoL completion please refer to section 6.6.1. PRO questionnaires (FACT-Lym, EQ-5D) should be administered *on Day 1 of alternate cycles during induction treatment period and at each cycle during maintenance treatment period. PRO Questionnaires should be administered on Day 1 of the cycle* prior to any treatment and assessments, i.e. *PRO questionnaires should be collected only when corresponding to a treatment cycle.* PRO questionnaires should also be administered at first assessment after report of disease progression.

^h AEs/SAEs/AESI/SSIRR/ADR that occur prior ICF signature should be reported in eCRF as available; however only the event preferred term as per CTCAE vs 5.0 is required as Individual Case Safety Report are not applicable. Prospective safety that must be fully assessed and reported by study physician including assessment of seriousness (see Section 8.1.1.2), severity (see Appendix 3), and causality (see Appendix 3).

ⁱ FLIPI score (age, number of nodal sites, LDH level, haemoglobin, stage) or FLIPI2 (age, beta-2 microglobulin, bone marrow involvement, longest diameter of largest involved node, haemoglobin) collected at diagnosis.

^j Response will be collected at mid of the induction (between 10 and 14 weeks after the start of treatments), end of the induction (at the day of cycle 6 until 1 month later) during maintenance (1 year after the start of treatment, i.e. from 10 to 14 months after the start of treatment; 2 years after the start of treatment, i.e. from 22 to 26 months after the start of treatment; 3 years after the start of treatment, i.e. from 34 to 38 months after the start of treatment), at the end of maintenance and at Follow-up as per clinical practice, as well as at any tumor assessment that shows disease progression, CR or CRu during induction or maintenance. The assessment of tumor response will be based on standard Cheson criteria and the Deauville 5-point scale (Appendix 6) (Younes et al. 2017).

^k All adverse events data available in medical records after start of the treatment should be reported until 185 days after the last obinutuzumab dose or until starting a new anti-cancer therapy (whichever occurs first). After this period AEs that are believed to be related to prior study drug treatment will be collected.

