Although Obinutuzumab has resulted to be generally well tolerated, IRRs have been reported with the use of the product, however occurring predominantly during infusion of the first 1,000 mg. These events will be closely monitored during the study and appropriate measures for prevention of IRRs (adequate glucocorticoid, oral analgesic/anti-histamine, omission of antihypertensive medicine in the morning of the first infusion, and the Cycle 1 Day 1 dose administered over 2 days) will be used in the study to reduce the incidence of IRRs, as scheduled in the current SmPC of the product. All AEs will be duly monitored in the study and appropriate measures (including the discontinuation of treatment with Obinutuzumab) will be implemented for the protection of patients' healthcare.

Therefore, treatment with Obinutuzumab offers the potential for clinical benefit in patients with untreated advanced FL for which the treating physician has decided to start treatment with Obinutuzumab.

Patients will be fully informed of the potential risks in taking part in this study, and investigators will make a careful assessment of the potential benefits and risks of Obinutuzumab, by monitoring the clinical status of the patient and the potential occurrence of AEs events and toxicities.

Therefore, the current evidence on the efficacy and safety of Obinutuzumab administered according to the therapeutic indication for the drug in patients with

untreated advanced FL suggest that the benefits that can be achieved from the participation in this observational study will outweigh the potential risks.

This trial will be conducted in compliance with the Declaration of Helsinki (1964 and amendments) current with the Good Pharmacoepidemiology Practice (GPP) published by the International Society of Pharmacoepidemiology (ISPE) and all other applicable laws and regulations.

For information on the condition under observation and on the Obinutuzumab please refer to the ~~Investigator's Brochure~~ and to the most recent version of the Summary of Product Characteristics (SmPC) of Gazyvaro®, i.e. the brand name of Obinutuzumab, for further details on nonclinical and clinical studies.

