Retrospective data applicable to the study includes but not limits to the following information available before ICF signature (enrolment):

- Information regarding previous cycles performed with Obinutuzumab and chemotherapy (at least 2 cycles and no longer than 1 year of treatment)
- Safety data
- Baseline condition (before start of the treatment)
- Medical history
- Relevant laboratory exams
- Concomitant medication and procedures
- Diagnostic information
- Tumor assessments and cancer history
- Imaging exams
- Demographic Data
- Physical exams, performance status and FLIPI classification

Data will be collected as availability in source document.

Safety data will be provided as aggregate data for retrospective visits. Minimal information such as the event term, seriousness classification and reason, relationship and duration of the event will be collected as available. For prospective data collection of safety, additional variables will be collected as available, such as grade, outcome, concomitant treatment, background causality, onset and end date.

Quality of life will be evaluated by means of the EuroQol 5-Dimension Questionnaire, 5-level version (EQ-5D-5L), and of the Functional Assessment of Chronic illness Therapy-Lymphoma (FACT-Lym).

The EuroQol 5-Dimension Questionnaire, 5-level version (EQ-5D-5L) (Appendix 4), is a validated self-report health status questionnaire that is used to calculate a health status utility score for use in health economic analyses (*EuroQol Group 1990; Brooks 1996; Herdman et al. 2011*).

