3.3.1 Adverse events

Adverse events are those with start date beyond or equal to the date of first administration of Obinutuzumab and until 185 days after the last Obinutuzumab dose intake or until starting a new anti-cancer therapy (whichever occurs first). After this period AEs that are believed to be related to prior study drug treatment will be collected.

All adverse events will be assigned to a Preferred Term (PT) and will be classified by primary System Organ Class (SOC) according to the MedDRA thesaurus version 22 or higher. Summary statistical tables including frequency counts and percentages and the number of adverse events will be produced.

Data will be listed by study site, patient number, and study day. Events occurring on or after treatment on Day 1 (treatment-emergent adverse events - TEAEs) will be summarized by mapped term, appropriate thesaurus levels, and NCI CTCAE v5.0 grade. In addition, SAEs, including deaths, will be listed separately and summarized.

AEs leading to treatment discontinuation will be listed.

Infusion related reactions (IRRs) and adverse events of special interest (AESI) will be summarized by descriptive statistics and will be listed.

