3.7 LIMITATIONS OF THE RESEARCH METHOD

This study will be conducted in approximately 50 sites in Italy and will reflect the standard of care in place in the selected investigational study sites. Therefore, caution should be used in the generalisation of data collected in this study.

Furthermore, the design of the trial may be associated with further limitations:

- the possible bias in patients' selection due to the uncontrolled design of the trial may have impact on results;
- as when entering in the initial patient's treatment/pre-treatment data are collected retrospectively, missing data might occur in the retrospective period as well the distribution of missing data might be different across the participating investigational sites;
- pooling of prospective and retrospective data collection will be done even though not equivalent and this needs to be taken into consideration when interpreting the results;
- COVID19 pandemic may have impact on routine clinical care.

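### Grade and onset date are not required for adverse events before consent, which include every first infusion, yet all events are pooled and summarised by CTCAE grade with no rule for missing grade

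*Protocol*

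**What the plan says.** **Timing of consent.** Protocol 6.2 admits patients who sign consent after at least two cycles of induction and within one year of starting treatment.

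**Data before consent.** Protocol Appendix 2 note h says events before consent are reported as available, but "however only the event preferred term as per CTCAE vs 5.0 is required". SAP Appendix 1 note h repeats this. Protocol 6.4.2 describes more for the same period: "Minimal information such as the event term, seriousness classification and reason, relationship and duration of the event will be collected as available". It then turns to the other period: "For prospective data collection of safety, additional variables will be collected as available, such as grade, outcome, concomitant treatment, background causality, onset and end date". Grade and onset date are named only there.

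**Passages that point the other way.** Protocol 6.4.4 has clinical adverse events recorded with the physician's severity assessment. Protocol 8.1.2 asks for a severity assessment of each event in the adverse event section of the CRF. Protocol 8.1.2.1 includes available events between treatment start and enrolment.

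**Analysis.** Under SAP 3.3.1, events on or after treatment on Day 1 "will be summarized by mapped term, appropriate thesaurus levels, and NCI CTCAE v5.0 grade". Protocol 6.7.2 adds that a repeated event takes the worst grade and strongest relationship within the patient. The safety population is everyone enrolled (SAP 3.1). SAP 3.7 says that "pooling of prospective and retrospective data collection will be done even though not equivalent". SAP 3.4 plans no sensitivity analyses and SAP 3.6 no handling of missing values. The output list in SAP Appendix 2 shows one summary and one listing of adverse events and IRRs, with no split by period.

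**The concern.** The grade tables need a variable that is not required for part of the period they cover, and that part is not a random slice of treatment. Protocol 4.1 says IRRs have been reported with the product, "occurring predominantly during infusion of the first 1,000 mg", and says they will be closely monitored. The first infusion is also the one that every patient receives before consent.

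Safety in routine practice is a stated objective, and severity is one of the listed safety variables. If early events arrive without a grade and the table has no place for them, a reader cannot tell a low grade 3 or higher rate from a poorly recorded one. Sites also have conflicting instructions, so the share of missing grades may differ between centres.

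**Working it through.** **1. The plan's own figures.** No precision or expected value is given for any grade rate, so there is no stated figure to reproduce on this point. The headline precision does reproduce: exact Clopper-Pearson limits for 39/300 are 9.41% to 17.34%, width 7.93% (stated 7.9%). Missing grades do not affect it.

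**2. What always precedes consent.** On the schedule in Synopsis Table 1, two cycles contain 3 + 1 = 4 infusions. That is 4 of 8 induction infusions with six cycles (3 + 5) and 4 of 10 with eight (3 + 7).

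**3. Direction.** Let G be the number of patients whose worst true grade is 3 or higher, and m the number of these who have no such grade on record. Over N enrolled, the table shows (G − m)/N, which cannot exceed G/N.

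**4. Illustration for IRRs.** Let e be the share of IRRs before consent and k the share of those with a recovered grade, the same for all grades. Then

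shown rate = true rate × [(1 − e) + e × k].

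From the documents: N = 300, and 59.3% with infusion-related events attributed to Obinutuzumab in the phase III trial (Protocol 4), so 0.593 × 300 ≈ 178 patients. Assumed, because the documents give no figure: 10% of these are grade 3 or higher, so the true rate is 17.8/300 = 5.9%. The values of e and k are also assumed.

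| e | k = 0 | k = 0.5 | k = 1 |
|---|---|---|---|
| 80% | 1.2% | 3.6% | 5.9% |
| 90% | 0.6% | 3.3% | 5.9% |
| 95% | 0.3% | 3.1% | 5.9% |

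At e = 90%, k = 0.5: (1.78 + 16.02 × 0.5)/300 = 9.79/300 = 3.3%. At k = 0: 1.78/300 = 0.6%. If 5% are grade 3 or higher, a true 3.0% shows as 1.6% (k = 0.5) or 0.3% (k = 0). If 20% are, a true 11.9% shows as 6.5% or 1.2%.

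**5. Bounds in the same illustration (e = 90%).** Counting every ungraded IRR as grade 3 or higher gives (1.78 + 160.2)/300 = 54.0% at k = 0 and (9.79 + 80.1)/300 = 30.0% at k = 0.5. The best-case bounds are the 0.6% and 3.3% above.

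**6. If only graded IRRs are the denominator (e = 90%, true share 10%).** Before consent there are 16.02 severe and 144.18 milder cases; after consent 1.78 and 16.02.
- All severe cases graded, half of the milder pre-consent ones: 17.8/(17.8 + 16.02 + 72.09) = 16.8%.
- Half of the severe pre-consent cases graded, all milder ones: 9.79/(9.79 + 160.2) = 5.8%.

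The error can go either way.

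**7. All grade 3 to 5 events.** At the phase III rate of 74.6%, 224 of 300 patients are affected (74.7%; exact 95% CI 69.3% to 79.5%). If 5% of these lose all their qualifying grades, the table shows 213/300 = 71.0%. If 10% do, it shows 201/300 = 67.0%, already below that interval.

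**The case against.** The strongest reply is that the plan nowhere bars grade before consent. Note h sets a minimum. Note k of the same appendix asks for all adverse event data available in the records, the field lists in 6.4.2 are examples, 8.1.2 wants severity for each recorded event, and Appendix 3.3.1 provides a dedicated form for the signs and symptoms of IRRs. This stands. A reader might infer that severity is unknown before consent; the documents support only that it is not required and may be missing.

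Other parts of the reply also stand:
- A reader might infer that nearly all IRRs are affected. The protocol gives no percentage for the first infusion, and says most reactions were grade 1 or 2.
- A reader might infer that grade rates are understated outright. No denominator is stated for the grade tables, and step 6 shows that the direction depends on it.
- Early neutropenia may be gradable from neutrophil counts, since retrospective laboratory data are collected and SAP 3.3.2 grades laboratory data.
- A missing onset date rarely decides inclusion, because retrospective events fall after treatment start by definition. It could matter at the end of the window for patients who stopped or changed therapy well before consent, and it affects listings by study day.
- The appendix has a separate row for retrospective safety data and 6.4.2 speaks of aggregate data, so the two streams can probably be told apart. The templates in SAP Appendix 3 were not available to check.

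The limitation in SAP 3.7 does not answer the point. It is general, does not mention grade and changes no table. Seriousness, which note h does not require either, cannot replace grade: Appendix 3.1 makes grade 4 and 5 events serious, but that does not identify grade 3.

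**Conclusion.** The point holds as a mismatch between the data required and the tables planned. Before consent, grade and onset date may be missing, and instructions to sites conflict. The pooled summary by grade has no rule for missing grade and no stated denominator. With all enrolled patients as denominator, missing grades can only lower grade-specific rates, chiefly for IRRs; with graded events only, the direction is unknown.

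The size cannot be computed, because neither the recovery of grades from charts nor the grade 3 or higher share of IRRs is given. The fall from 5.9% to 3.3% or 0.6% rests on the assumed 10% and 90% and on recovery unrelated to grade. If all grades are recovered, there is no bias.

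Incidence by preferred term is not affected by missing grade, and the POD24 and PFS precision is untouched. This is a cheap improvement to the safety reporting; a bias has not been demonstrated.

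**What to change.** - **Reconcile the instructions.** Align note h (Protocol Appendix 2 and SAP Appendix 1) with Protocol 6.4.2, 6.4.4, 8.1.2 and 8.1.2.1, so that one statement says which fields are sought before consent.
- **Retrieve what exists.** Request grade and onset date for pre-consent IRRs and serious adverse events where the chart records them. This needs no new visits or source data.
- **Change SAP 3.3.1.** Present adverse events by collection period (retrospective, prospective) as well as overall. Keep retrieved retrospective grades and relatedness; restricting grade tables to the prospective period would discard the IRR grades just retrieved. Add a grade-unknown row and state the denominator.
- **Show the uncertainty.** For grade 3 or higher rates, give a best case (all ungraded events below grade 3) and a worst case (all at grade 3 or higher). The bounds will be wide if few grades are recovered, which is a reason to do the chart look-up first.

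The cost is more adverse event tables, a correction to the notes and limited chart look-up.
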